1. PROTOCOL SUMMARY

1.1. Synopsis

CicloMed LLC
[name]
[name]
[name]

| | |
|-------------------------------|--|
| Study Title: | A Phase 1, First-in-Human, Safety, Dose Tolerance, Pharmacokinetics, and Pharmacodynamics Study of CPX-POM in Patients with Advanced Solid Tumors |
| IND Number: | 132545 |
| Study Centers Planned: | Approximately 6 centers in the United States |
| Objectives: | 
The primary objective of this study is as follows:
 
• To evaluate the dose limiting toxicities (DLTs) and maximum tolerated dose (MTD) of ciclopirox phosphoryloxymethyl ester (CPX-POM) administered intravenously (IV) and establish the CPX-POM dose recommended for further investigation. 
The secondary objectives of this study are as follows:
 
• To characterize the plasma and urine pharmacokinetics (PK) of CPX-POM and its metabolites following single and multiple dose administration;• To identify preliminary anti-tumor activity of CPX-POM;• To determine urine β-glucuronidase activity in patients participating in the trial. 
The exploratory objectives of this study are as follows:
 
• To characterize the pharmacologic effects of CPX-POM on circulating biomarkers of Wnt and Notch cell signaling pathways;• To explore pharmacodynamic (PD) relationships between changes in circulating biomarkers and drug and/or metabolites exposure and other outcomes. |
| Study Design: | 
This is a first-in-human, Phase 1, multicenter, open label, dose escalation study to evaluate the DLTs and MTD and to determine the recommended Phase 2 dose (RP2D) of CPX-POM administered IV in patients with any histologically- or cytologically-confirmed solid tumor type. Secondary objectives include characterization of the safety and PK profile of CPX-POM and identification of preliminary anti-tumor activity in this patient population. Biomarkers and their relationship to PK and other outcomes will be examined as an exploratory objective.
 
The study will initially employ an accelerated escalation design, with a single patient enrolled in each cohort (i.e., Single-Patient Cohorts). The initial patient cohort will receive CPX-POM at a starting dose of 30 mg/m². Doses will be escalated in 100% increments (i.e., doubling), until a \geqGrade 2 toxicity (with the exception of alopecia), as determined according to the United States (US)
 |

National Cancer Institute (NCI) Common Terminology Criteria for Adverse Events (CTCAE), version 4.03, is encountered, at which point that cohort and all subsequent cohorts will follow a classical “3 + 3” dose escalation design (i.e., Standard Dose Escalation Cohorts).

After each cohort is completed, a Safety Review Committee (SRC) comprised of the CRO Medical Monitor, Principal Investigator(s), and Sponsor representatives will meet to discuss the data and decide upon the next dose escalation. Doses in the standard cohorts will be escalated in 25 to 50% increments, based on SRC decision, until the MTD is reached. In addition, after completion of Cycle 1 for the first 4 to 6 patients, the SRC will review safety, PK, and PD data to determine if any changes to the dosing schedule are indicated.

Inpatient dose escalation will not be allowed in any patient at any time.

Each patient in a dose cohort must have received at least 80% of their CPX-POM doses, unless due to toxicity, during Cycle 1 with follow-up safety evaluations through Day 22 (or Cycle 2, Day 1, if continuing in the study) to be eligible for the assessment of DLT.

Patients may continue to receive cycles of CPX-POM until progression of disease, intolerable toxicity occurs, or another withdrawal criterion applies.

Approximately 24 patients will be enrolled in the Single-Patient and Standard Dose Escalation Cohorts to establish the MTD. In addition to these estimated 24 patients, Expansion Cohort(s) may be enrolled after the MTD is reached to either explore different dosing schedules, increase the experience with a particular tumor type (e.g., muscle invasive bladder cancer [MIBC]), or to examine the safety and anti-tumor activity of CPX-POM in combination with certain other anticancer agents.

Dose escalation procedures will be conducted as follows:

Accelerated Titration (Single-Patient Cohorts; n=1 each)

- | | |
|--|---|
| No \geq Grade 2 adverse events (AEs) | 
• Continue evaluation of single-patient dose cohorts.• Escalate by 100% to next dose level. |
| At least 1 \geq Grade 2 AE not meeting the definition of DLT | 
• Expand current and subsequent cohorts to at least 3 patients (see Standard Dose Escalation Scheme below). |
| 1 DLT | 
• Expand current cohort up to 6 patients or until 2 DLTs are encountered (Standard Dose Escalation Scheme below). |

Standard Dose Escalation (Standard Cohorts; n=3 to 6 each)

- | | |
|--------------------------------|--|
| No DLT | 
• Escalate by 25–50% to next dose level. |
| 1 DLT in \leq 3 patients | 
• Expand cohort up to 6 patients. |
| 1 DLT in 6 patients | 
• Escalate by 25–50% to next dose level. |
| $>$ 1 DLT in \leq 6 patients | 
• MTD reached; stop dose escalation.• Possibly explore intermediate doses for the RP2D. |
-

A Dose-Limiting Toxicity will be defined as any of the following if deemed related to study drug:

- Grade 4 thrombocytopenia of any duration
- Grade 3 thrombocytopenia with significant hemorrhage of any duration
- Grade 4 absolute neutrophil count (ANC) >5 days
- Febrile neutropenia
- Grade ≥ 3 non-hematologic toxicity of any duration, except:
 - Grade 3 nausea, vomiting, or diarrhea and Grade 4 vomiting or diarrhea in the absence of maximal medical therapy that resolves in 72 hours
 - Grade 3 fatigue lasting <5 days
 - Grade 3 hypertension that can be controlled with medical therapy
 - An increase of indirect (unconjugated) bilirubin indicative of M. Meulengracht/Gilbert’s syndrome
 - Serum lipase and/or serum amylase CTCAE Grade 3 ≤ 7 consecutive days without clinical signs or symptoms of pancreatitis
- Delay in study drug due to toxicity for >2 weeks
- Alanine aminotransferase (ALT)/aspartate aminotransferase (AST) >3xULN with bilirubin >2x the upper limit of normal (ULN) without another explanation (e.g., cholestasis)

Any patient who is unable to receive 80% of the expected dose of CPX-POM (i.e., patients who are unable to receive at least 4 of the 5 scheduled doses) because of AEs will be considered to have a DLT.

| | |
|------------------------------------|---|
| Number of Patients Planned: | Approximately 24 patients will be enrolled in dose escalation cohorts to establish the MTD. In addition to these estimated 24 patients, Expansion Cohort(s) may also be enrolled after the MTD is reached. |
| Target Population: | Patients with any histologically- or cytologically-confirmed solid tumor type that is refractory to standard therapy. Patients should only be included if no therapy exists or if they have received all standard therapies that would be potentially curative or might provide significant benefit. |
| Duration of Study: | Patients who receive one treatment cycle will be in this study for up to approximately 8 weeks: up to a 28-day Screening period, a 21-day Treatment cycle, and a Follow-up period out to 28 ± 5 -days after the last dose (i.e., approximately Day 33). After the first treatment cycle, patients may continue to receive cycles of CPX-POM until progression of disease, intolerable toxicity occurs, or another withdrawal criterion applies. |

| | |
|---|---|
| Diagnosis and Main Eligibility Criteria: | 
Patients eligible for enrollment in this study will be adults with any histologically- or cytologically-confirmed metastatic or advanced-stage solid tumor that is refractory to standard therapy. Patients should only be included if no therapy exists or if they have received all standard therapies that would be potentially curative or might provide significant benefit. Patients must have a life expectancy ≥ 3 months, an Eastern Cooperative Oncology Group (ECOG) Performance Status 0 or 1, no significant ischemic heart disease, adequate hepatic function, and a baseline glomerular filtration rate (GFR) > 50 mL/min/1.73m². Females must not be pregnant and, if of childbearing potential, must use an effective method of contraception to avoid pregnancy during and for 3 months after participation in the trial.
 
Patients who have any risk factor for torsade de pointes or any uncontrolled or severe intercurrent medical condition, or who have had major surgery or prior systemic chemotherapy or radiation therapy within the previous 4 weeks are excluded.
 |
| Test Product, Dose, and Mode of Administration: | 
Escalating doses of CPX-POM will be administered by 10-minute IV infusion once daily on Days 1-5 of each 21-day cycle.
 
After completion of Cycle 1 for the first 4 to 6 patients, the SRC will review safety, PK, and PD data to determine if any changes to the dosing schedule are indicated (e.g., adding an additional 5 days of dosing to each treatment cycle).
 
Patients may continue to receive cycles of CPX-POM until progression of disease, intolerable toxicity occurs, or another withdrawal criterion applies. The starting dose will be 30 mg/m².
 |
| Reference Therapy, Dose, and Mode of Administration: | 
Not applicable.
 |
| Criteria for Evaluation: | 
Safety:
 
Safety and tolerability will be based on an assessment of AEs, physical examinations, vital signs, electrocardiograms (ECGs), clinical laboratory tests, ophthalmologic assessments, and concomitant medications.
 
The MTD will be defined as the dose BELOW that dose which causes DLTs in $\geq 33\%$ of patients.
 
Pharmacokinetics:
 
Serial blood (plasma) samples and complete urine will be collected over 24-hour periods starting after the first (Day 1) and fifth (Day 5) doses of CPX-POM during Cycle 1 to characterize single dose and steady-state plasma and urine PK of CPX-POM, ciclopirox (CPX), and ciclopirox glucuronide (CPX-G). If patients are unable or unwilling to attend the required 12 hours of clinic visitation required for steady-state PK sampling on Day 5 of Cycle 1, the steady-state PK sampling may be postponed to Day 5 of Cycle 2. Urine β-glucuronidase activity will be measured prior to and after 5 days of CPX-POM administration (i.e., on Days 1 and 5 of Cycle 1).
 
Pharmacodynamics:
 
Blood will be collected to characterize the effects of CPX-POM on circulating biomarkers of Wnt and Notch cell signaling pathways. Plasma and peripheral blood mononuclear cells (PBMCs) will be isolated from blood. Vascular
 |

endothelial growth factor (VEGF), interleukin (IL)-6, and IL-8 concentrations will be measured in plasma by enzyme-linked immunoassay (ELISA). Quantitative real-time polymerase chain reaction (qRT-PCR) will be used to characterize gene expression of circulating biomarkers of Wnt and Notch signaling pathways in PBMCs.

**Statistical
Methods:**

Safety:

Safety data will be presented in by-patient listings. Categorical safety endpoints will be summarized by frequency of events/abnormalities for each dose group and overall. Continuous safety endpoints will be summarized using descriptive statistics (number of subjects [n], mean, standard deviation, median, first quartile [Q1], third quartile [Q3], minimum, maximum) for each dose group and overall.

Pharmacokinetics:

Standard PK parameters will be derived from resultant plasma and urine drug and metabolite concentration-time data using non-parametric methods. PK parameters will be summarized using descriptive statistics.

Pharmacodynamics:

[figure not shown]
A logistic regression will be used to estimate the predicted toxicity probability at each dose level. Relationships between dose, drug and metabolite exposure, PD response, and other endpoints (i.e., ECGs, toxicity, safety, and biomarker endpoints) may be explored using descriptive statistics, and/or additional PK/PD modeling.

This study will be conducted in accordance with the guidelines of current GCPs including archiving of essential documents.

1.2. Study Diagram

The study design is illustrated in Figure 1.

Figure 1. Study Design

Abbreviations: CPX-POM = ciclopirox phosphoryloxymethyl ester; D = day; PD = pharmacodynamic; PK = pharmacokinetic; V = visit.

1.3. Schedule of Assessments

The schedule of assessments is shown in Table 1.

Table 1. Schedule of Assessments

| Study Procedure | Screening Period | Treatment Period | | | | | | | | Follow-up Period ⁵ |
|---|---------------------------------|------------------|----|----|----|-----------------|----|------------------------------------|----------------------------------|---|
| | Study Days: D -28 to D -1 | D1 ¹ | D2 | D3 | D4 | D5 ¹ | D6 | D10 ² (Cycle 1 only) | D22 (last cycle) ⁴ | 28 (±5) days post last dose or at early termination |
| | Study Visits: V1 | V2 | V3 | V4 | V5 | V6 | V7 | V8 | | |
| Informed consent | X | | | | | | | | | |
| Inclusion/exclusion criteria | X | X | | | | | | | | |
| ECOG Performance Status | X | | | | | | | | | X |
| Medical history | X | | | | | | | | | |
| HIV and hepatitis screening ⁶ | X | | | | | | | | | |
| Pregnancy test ⁷ | X | X | | | | | | | | |
| Cancer evaluation ⁸ | X | X | | | | | | | | |
| CT or MRI | X | | | | | | | | | |
| MUGA or ECHO | X | | | | | | | | | |
| Hematology ⁹ | X | X | | | X | | | X | X | X |
| Clinical chemistry ¹⁰ | X | X | | | X | | | X | X | X |
| Thyroid panel ¹¹ | X | X | | | | | | | | |
| Coagulation test ¹² | X | X | | | | | | | | |
| Urinalysis ¹³ | X | X | | | | X | | X | X | X |
| Full physical exam ¹⁴ | X | | | | | | | | | X |
| Assess for physical symptoms/toxicities ¹⁵ | | X | X | X | X | X | X | X | X | |
| Ophthalmologic exam ¹⁵ | X | | | | | | | | | X |
| Vital signs ¹⁶ | X | X | X | X | X | X | X | X | X | X |
| ECG ¹⁷ | X | X | | | | X | | | | X |
| Start 24- hour Holter monitor ¹⁸ | | X | | | | | | | | |

| Study Procedure | Screening Period | Treatment Period | | | | | | | | Follow-up Period ⁵ |
|--|------------------|------------------|----|----|----|-----------------|----|---------------------------------|-------------------------------|---|
| | D -28 to D -1 | D1 ¹ | D2 | D3 | D4 | D5 ¹ | D6 | D10 ² (Cycle 1 only) | D22 (last cycle) ⁴ | 28 (±5) days post last dose or at early termination |
| Study Days: | V1 | V2 | V3 | V4 | V5 | V6 | V7 | V8 | | |
| Adverse events | X | X | X | X | X | X | X | X | X | X |
| Concomitant medications | X | X | X | X | X | X | X | X | X | X |
| PK blood samples ¹⁹ | | X | X | | | X | X | | | |
| PK urine samples ²⁰ | | X | X | | | X | X | | | |
| β glucuronidase urine sample ²¹ | | X | | | | X | | | | |
| Biomarker blood sample ²² | | X | | | | X | | | X | X |
| Body surface area ²³ | | X | | | | | | | | |
| CPX-POM infusions ²⁴ | | X | X | X | X | X | | | | |

Abbreviations: ALP = alkaline phosphatase; ALT = alanine aminotransferase; aPTT = activated partial thromboplastin time; AST = aspartate aminotransferase; BSA = body surface area; BUN = blood urea nitrogen; CPX-POM = ciclopirox phosphoryloxymethyl ester; CT = computed tomography; D = day; ECG = electrocardiogram; ECOG = Eastern Cooperative Oncology Group; EDTA = ethylenediamine tetraacetic acid; eGFR = estimated glomerular filtration rate; GGT = gamma glutamyl transferase; HIV = human immunodeficiency virus; IV = intravenous; MUGA = multi-gated acquisition; MRI = magnetic resonance imaging; PBMC = peripheral blood mononuclear cell; PD = pharmacodynamic; PK = pharmacokinetic; PT = prothrombin time; RBC = red blood cell; T3 = triiodothyronine; T4 = thyroxine; TSH = thyroid stimulating hormone; V = visit; WBC = white blood cell.

1. On Days 1 and 5 of Cycle 1, patients will be required to stay at the clinical research unit for at least 12 hours for PK sampling and other assessments. If patients are unable or unwilling to attend the required 12 hours of clinic visitation required for steady-state PK sampling on Day 5 of Cycle 1, the steady-state PK sampling may be postponed to Day 5 of Cycle 2. To shorten the duration of the Cycle 1, Day 1 visit, if needed, the safety laboratory blood samples required for this visit may be drawn up to 3 days before Day 1.
2. The Day 10 (Visit 8) study visit will only be required during Cycle 1.
3. After cycle 1; visit windows can be considered on a case by case basis due to events such as holidays; Cycle 1 needs to occur without visit windows. D6 can occur +2 calendar days for cycles after Cycle 1 is completed.
4. If final treatment cycle, patient returns for assessments on Day 22. If additional cycles are planned, patient skips this visit and restarts schedule at Day 1 (except for PK). Patients may continue to receive cycles of CPX-POM until progression of disease, intolerable toxicity occurs, or another withdrawal criterion applies.

5. The Follow-up visit will occur 28±5 days after the last dose of CPX-POM administered during the last treatment cycle. Or, in the event that a patient discontinues from the study prematurely, the site will make every effort to perform the assessments listed for this study visit.
6. Hepatitis screening will include tests for Hepatitis A, Hepatitis B, and Hepatitis C.
7. Pregnancy tests will be required only for women of child bearing potential at Screening and before dosing on Day 1 of each treatment cycle. Urine or serum pregnancy tests are acceptable.
8. Cancer evaluation will include determination of staging and metastases for screening purposes (see Section 8.1). Disease response assessments will be performed for patients with measurable disease within 28 days prior to the first dose of CPX-POM and repeated at the end of every second cycle (i.e., at approximately 6-week intervals). During the Dose-Escalation Phase of the study, Screening cancer evaluations may be performed up to 28 days before Cycle 1, Day 1. For patients enrolled in any Expansion cohorts, Screening cancer evaluations must be performed within 28 days of Cycle 1, Day 1.
9. Hematology will include measurement of hemoglobin, hematocrit, platelets, RBC, reticulocytes, and WBC with differential. To shorten the duration of the Cycle 1, Day 1 visit, if needed, the safety laboratory blood samples required for this visit may be drawn up to 3 days before Day 1 (Cycle 1 only).
10. Clinical chemistry will include measurement of potassium, sodium, chloride, glucose, BUN, creatinine, creatinine clearance, ALT, AST, ALP, GGT, alkaline phosphatase, indirect bilirubin, direct bilirubin, total bilirubin, total protein, albumin, calcium, bicarbonate, magnesium, phosphate, lipase, and amylase. To shorten the duration of the Cycle 1, Day 1 visit, if needed, the safety laboratory blood samples required for this visit may be drawn up to 3 days before Day 1.
11. Thyroid panel will include TSH, free T4, and free and total T3 and will be repeated on D1 of each cycle.
12. Coagulation tests will include PT and aPTT and will be repeated on D1 of each cycle.
13. Urinalysis will include color, turbidity, pH, specific gravity, glucose, ketones, nitrites, bilirubin, urobilirubin, protein, RBCs, WBCs, epithelial cells, casts, crystals, and bacteria, and eGFR at Screening only.
14. A full physical examination will be conducted at Screening and at Follow-up. At each other study visit, patients will be assessed for continued dosing and any possible physical symptoms/toxicities and a physical examination may be performed, if indicated. Body weight should be measured at each study visit. Height should be measured at Screening.
15. Ophthalmology evaluations will be conducted at least on Day 1 and at Follow-up by a qualified ophthalmologist and will include visual acuity, pupil exam, confrontation visual field, extraocular motility and alignment, interior slit lamp examination, and dilated fundus examination of the retina. Additional ophthalmology evaluations may be performed at any other time, if indicated, as determined by the investigator.
16. Vital signs will be measured before any blood draws scheduled for the same time point. Vital signs will include blood pressure, respiratory rate, pulse, oxygen saturation, and temperature. On Days 1 and 5, vital signs will be measured at pre-dose and at 6-hour intervals post-dose.
17. At Screening, 12-lead ECGs will be performed in triplicate, with each measurement separated by 2 minutes. The average of the 3 screening ECGs will be used to calculate QTc interval to determine study eligibility. Thereafter, single 12-lead ECGs will be performed for all patients prior to drug administration on Days 1 and 5 of Cycle 1; on Day 1 of each subsequent treatment cycle; and at the Final Study visit.
18. **Cycle 1:** Starting on Day 1 of Cycle 1, digital Holter monitoring will be performed from 45 minutes pre-dose through 24 hours post-dose. ECG extractions of the continuous Holter recordings will be performed at 45, 30, and 15 minutes pre-dose and at specific post-dose time points

coinciding with the serial blood sampling time points for pharmacokinetics. Patients will be instructed to assume a supine position 5-10 minutes prior to each serial blood sampling time point and remain supine throughout the 5-minute ECG extraction period just prior to serial blood sample collection. During the 24-hour Holter monitoring period, a 12-lead ECG tracing may be printed out at any time while the patient is in the clinic at the discretion of the investigator. If for any reason Holter monitoring is not performed in conjunction with the PK sampling on Day 1 or the tracings are of poor quality, Holter monitoring may be performed in conjunction with the PK sampling on Day 5.

19. **Cycle 1:** Serial, 3-mL blood samples will be taken for determination of plasma CPX-POM and metabolites concentrations during Cycle 1 at 0.25, 0.5, 1.0, 1.5, 2.0, 3.0, 4.0, 5.0, 6.0, 8.0, 10.0, 12.0, and 24.0 hours following completion of the 10-minute IV infusion on Day 1 and on Day 5. Each PK sample should be collected as close as possible to the planned time. The 12.0 hour collection can have a +/- 1-hour window (collect within 11 to 13 hours) and the exact time must be recorded. The actual date and time of each blood sample collection will be accurately recorded.
20. **Cycle 1:** Complete 24-hour urine samples for determination of CPX-POM and metabolites concentrations, and measurement of urine volume will be obtained from each patient in urine collection and storage containers during Cycle 1. A sample will be taken at pre-dose on Day 1, and complete urine samples will be collected at 0-12 and 12-24 hour collection intervals post-dose on Days 1 and 5. The 12 hour collection can have a +/- 1-hour window (collect within 11 to 13 hours) and the exact time must be recorded.
21. **Cycle 1:** Urine β -glucuronidase activity will be determined in the complete 24-hour urine samples collected on Day 1 and Day 5 of Cycle 1.
22. 7-mL blood samples will be obtained in EDTA-containing blood collection tubes at pre-dose on Day 1 and Day 5 of each treatment cycle, and on Day 22 of the last treatment cycle. Plasma and buffy coat (PBMCs) will be isolated, transferred to storage tubes, and stored frozen.
23. BSA will be calculated by the site personnel using the Dubois method of calculation using screening height and baseline weight measurements. BSA is to be recalculated before study drug administration on Day 1 of every other treatment cycle, starting with Cycle 3 and the patient's study drug dose adjusted accordingly.
24. CPX-POM infusions will be administered once every 24 hours as 10-minute IV infusions on Days 1-5 of each 21-day treatment cycle. After completion of Cycle 1 for the first 4 to 6 patients, the SRC will review safety, PK, and PD data to determine if any changes to the dosing schedule are indicated (e.g., adding an additional 5 days of dosing to each treatment cycle).

GLOSSARY OF ABBREVIATIONS AND DEFINITION OF TERMS

| | |
|----------------------|---|
| AE | adverse event |
| ALT | alanine aminotransferase |
| ANC | absolute neutrophil count |
| aPTT | activated partial thromboplastin time |
| AST | aspartate aminotransferase |
| AUC | area under the concentration-time curve following a single dose on Day 1 |
| AUC _{ss} | area under the concentration-time curve over the dosing interval at steady-state following drug administration on Day 14 |
| AUC _[0-t] | area under the concentration-time curve following administration of a single dose on Day 1 |
| AUC _[t-∞] | area under the concentration-time curve following administration of a single dose on Day 1 from the last quantifiable concentration (t) to infinity |
| AUC _{inf} | area under the curve from time zero to extrapolated infinite time [AUC(0 ∞)] following administration of a single dose on Day 1 as the sum of AUC[0-t] + AUC(t-∞) |
| BSA | body surface area |
| CL _r | single dose (Day 1) and steady-state (Day 14) renal clearance |
| CL _s | systemic clearance following administration of a single dose on Day 1 |
| CL _{ss} | systemic clearance at steady-state |
| C _{max} | the maximum observed serum/plasma/PBMC concentration of drug |
| C _{SSmax} | the maximum observed plasma concentration of drug and metabolites observed at steady-state over the dosing interval |
| CPX | ciclopirox |
| CPX-G | ciclopirox glucuronide |
| CPX-O | ciclopirox olamine |
| CPX-POM | ciclopirox phosphoryloxymethyl ester (ciclopirox prodrug) |
| CRF | case report form(s) |
| CRO | contract research organization |
| CT | computed tomography |
| CTCAE | Common Terminology Criteria for Adverse Events |
| DLT | dose limiting toxicity |
| ECG | electrocardiogram |
| ECOG | Eastern Cooperative Oncology Group |
| ELISA | enzyme-linked immunoassay |

| | |
|----------|--|
| FDA | (United States) Food and Drug Administration |
| GCP | Good Clinical Practice |
| GFR | glomerular filtration rate |
| GGT | gamma glutamyl transferase |
| GLP | Good Laboratory Practices |
| HNSTD | highest non-serious toxic dose |
| IB | Investigator's Brochure |
| ICF | informed consent form |
| ICH | International Council on Harmonisation |
| IL | Interleukin |
| IRB | institutional review board |
| IV | intravenous |
| LC-MS/MS | liquid chromatography tandem mass spectroscopy |
| MedDRA | Medical Dictionary for Regulatory Activities |
| MIBC | muscle invasive bladder cancer |
| mRNA | messenger RNA |
| MTD | maximum tolerated dose |
| MUGA | multi-gated acquisition |
| n | number of subjects |
| NCI | National Cancer Institute |
| NOAEL | no observed adverse effect level |
| PBMC | peripheral blood mononuclear cell |
| PD | pharmacodynamic |
| PK | pharmacokinetic |
| PT | prothrombin time |
| Q1 | first quartile |
| Q3 | third quartile |
| qRT-PCR | quantitative real-time polymerase chain reaction |
| QTc | corrected QT interval |
| QTcF | QT interval corrected using Fridericia's formula |
| RECIST | Response Evaluation Criteria for Solid Tumors |
| RNA | ribonucleic acid |
| RP2D | recommended phase 2 dose |
| SAE | serious adverse event |
| SOC | system organ class |

| | |
|--------------|---|
| SRC | Safety Review Committee |
| SUSAR | suspected unexpected serious adverse reaction |
| t_{\max} | the time (observed time point) of C_{\max} |
| $t_{SS\max}$ | the time (observed time point) of C_{\max}^{SS} |
| $t_{1/2}$ | apparent elimination half-life |
| ULN | upper limit of the normal range |
| US | United States |
| Vd | apparent volume of distribution |
| VEGF | vascular endothelial growth factor |
| Vss | Steady-state volume of distribution |
| λ | apparent first-order elimination rate constant |

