6.1.5. Dose Modifications

If a patient develops a DLT, CPX-POM dosing should be discontinued until the toxicity is resolved (see definition of a DLT in Section 4). If the toxicity resolves to at least Grade 1, treatment may be re-initiated and the dose of CPX-POM should be reduced by one dose level. If a patient has a second episode of the same DLT despite dose reduction, they should be permanently discontinued from study.

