9.6. Pharmacokinetic Analysis

9.6.1. Pharmacokinetics in Plasma

Plasma concentrations of CPX-POM and its metabolites will be determined by GLP-validated liquid chromatography tandem mass spectroscopy(LC-MS/MS) assays. Analysis of resultant plasma CPX-POM (and its metabolites) concentration-time data will be performed using non-parametric PK data analysis methods using Phoenix WinNonlin 7.0 (Certara LP, Princeton, NJ). PK parameters will be listed and summarized for each analyte using descriptive statistics (e.g., sample size, arithmetic mean, % coefficient of variation, standard deviation, median, minimum, and maximum). The following PK parameters will be determined:

- C_{max} - Maximum observed plasma concentration (C_{max}) observed following administration of a single dose on Day 1
- T_{max} - Time to reach maximum observed plasma concentration (C_{max})
- $AUC_{[0-t]}$ - Area under the concentration-time curve following administration of a single dose on Day 1
- $AUC_{[t-\infty]}$ - Area under the concentration-time curve following administration of a single dose on Day 1 from the last quantifiable concentration (t) to infinity.
- AUC_{inf} - Area under the curve from time zero to extrapolated infinite time [$AUC_{(0-\infty)}$] following administration of a single dose on Day 1 as the sum of $AUC_{[0-t]} + AUC_{(t-\infty)}$
- $C_{SS_{max}}$ - Maximum observed plasma concentration at steady-state on Day 5
- $T_{SS_{max}}$ - Time to reach maximum observed plasma concentration ($C_{SS_{max}}$) on Day 5
- AUC_{SS} - Area under the concentration-time curve over the dosing interval at steady-state following drug administration on Day 5
- λ - Apparent first-order elimination rate constant
- $t_{1/2}$ - Apparent elimination half-life
- Cl_s – Systemic clearance following administration of a single dose on Day 1
- Cl_{ss} – Systemic clearance at steady-state
- V_d – Apparent volume of distribution
- V_{ss} – Steady-state volume of distribution

- C_{max} Derived Accumulation Ratio - C_{SSmax}/C_{max}
- AUC Derived Accumulation Ratio - $AUC_{ss}/AUC_{(0-\infty)}$
- CL_r – Single dose (Day 1) and steady-state (Day 5) renal clearance

Plasma drug and metabolite concentration-time data and derived plasma PK parameters will be presented in tabular and graphic format.

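### If steady-state PK is postponed to Cycle 2, the D6 visit allowance conflicts with the 24-hour sample, and the accumulation ratios make no provision for a reduced dose

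*Protocol*

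**What the plan says.** **Postponement.** Table 1 footnote 1 provides that, for a patient who cannot or will not stay 12 hours on Day 5 of Cycle 1, "the steady-state PK sampling may be postponed to Day 5 of Cycle 2". The synopsis and Section 5.3 also provide for this.

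**Sample times.** Footnote 19 lists 13 plasma samples after each profiled dose, the last at "24.0 hours following completion of the 10-minute IV infusion on Day 1 and on Day 5". It asks for each sample as near its planned time as possible, requires actual times to be recorded, and gives a numerical tolerance only for the 12-hour sample (1 hour either way). Table 1 marks PK blood on D1, D2, D5 and D6, so the sample that closes the Day 5 profile falls on D6.

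**Visit windows.** Footnote 3 says "Cycle 1 needs to occur without visit windows", and then "D6 can occur +2 calendar days for cycles after Cycle 1 is completed". Neither footnote mentions a postponed profile.

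**Dose after a DLT.** Under Section 6.1.5, once the toxicity has resolved sufficiently, "treatment may be re-initiated and the dose of CPX-POM should be reduced by one dose level".

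**Parameters.** Section 9.6.1 defines AUCss as "Area under the concentration-time curve over the dosing interval at steady-state following drug administration on Day 5". Its accumulation ratios are CSSmax/Cmax and AUCss/AUC(0-∞), with no dose term.

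**Listing shells.** SAP Listing 16.2.6-2 (plasma) replicates Listing 16.2.6-1, whose rows are Cycle 1 Day 1 and Cycle 1 Day 5 only.

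**The concern.** The protocol keeps D6 fixed in Cycle 1, where the PK profile normally sits, and relaxes it in Cycle 2, the one later cycle to which the profile may move. A site could use the D6 allowance in good faith and draw the closing sample one or two days late. AUCss, steady-state clearance and the AUC ratio would then depend on how the analyst bridges the interval from 12 hours to the late sample, and Section 9.6.1 gives no rule for that.

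The dose problem is separate. Postponement puts a cycle boundary between the numerator and the denominator of each ratio. If the dose was cut in between, the ratio mixes accumulation with the dose change, and a summary by original cohort would attribute the profile to a dose the patient did not receive that day.

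**Working it through.** The documents state no half-life, AUC or accumulation ratio, so there is no figure of the plan's own to reproduce on this point. The Table 4 steps used below do check: 350/240 = 1.458, 475/350 = 1.357 and 600/475 = 1.263, against the stated 46%, 36% and 26%.

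**A. Late closing sample**

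Inputs: samples to 12 h on Day 5 as planned; closing sample at T = 24 h (on time), 48 h (D6 one day late) or 72 h (two days late). Assumed: one-exponential decline C(t) = exp(−kt) with k = ln 2 / half-life, and half-life 2 to 12 h. Earlier doses multiply every Day 5 concentration by the same constant, which cancels in a percentage error. No dose follows Day 5 on the stated schedule, so a late sample still belongs to the same decline.

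- Exact: AUC(0-24) = (1 − C24)/k.
- Linear interpolation: C24* = C12 + (C_T − C12) × 12/(T − 12).
- Estimate: (1 − C12)/k + 6 × (C12 + C24*).

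Example, half-life 6 h, T = 72 h: k = 0.1155, C12 = 0.25, C24 = 0.0625, C72 = 0.0002. The exact AUC is 0.9375/0.1155 = 8.115. C24* = 0.8 × 0.25 + 0.2 × 0.0002 = 0.200. The estimate is 6.492 + 6 × 0.450 = 9.192, an error of +13.3%.

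| Assumed half-life | On time, 24 h | 48 h | 72 h |
|---|---|---|---|
| 2 h | +1.8% | +3.9% | +4.3% |
| 4 h | +3.7% | +10.9% | +12.7% |
| 6 h | +3.1% | +10.9% | +13.3% |
| 8 h | +2.3% | +9.2% | +11.7% |
| 12 h | +1.3% | +6.1% | +8.4% |

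Using the linear rule over the whole profile, with the protocol's sampling times and the 10-minute infusion, gives similar values: +5.2, +13.0, +13.4, +11.8 and +8.4% at 72 h.

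Other rules give other answers for the same 72 h sample:
- Log interpolation from actual times: 0.0% at every half-life tried (1 to 24 h), because the model is log-linear.
- AUC to the last sample taken as the interval AUC: (1 − C72)/(1 − C24) − 1, which is +1.6% at 4 h, +6.6% at 6 h and +31% at 12 h.

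An AUCss error passes one for one into AUCss/AUC(0-∞). CSSmax/Cmax does not change, because all samples from 0.25 to 12 h are taken on Day 5 itself.

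**B. Reduced dose**

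Under linear PK, the un-normalised ratio equals the true ratio × (dose at the postponed profile / dose on Cycle 1 Day 1).

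| One-level reduction (mg/m²) | Multiplier |
|---|---|
| 240 to 120 (doubling step) | 0.50 |
| 350 to 240 | 240/350 = 0.69 |
| 475 to 350 | 350/475 = 0.74 |
| 600 to 475 | 475/600 = 0.79 |

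Both ratios are affected, whatever the half-life. Dividing each value by the mg infused removes the factor under linear PK. BSA adds no further change, since it is first recalculated at Cycle 3.

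**The case against.** The best answer on timing is that the two extra days are a visit allowance and not a sampling window. Footnote 19 still sets the sample at 24.0 hours, asks for it as near to plan as possible and has the actual time recorded. Footnote 4 also restarts later cycles without PK, so D6 of Cycle 2 carries no PK draw by default. This stands in part: the plan does not schedule a late sample. But a postponed profile has to be closed somewhere, D6 is the only Table 1 column for it, and nothing says which footnote prevails. Footnote 19 is also headed Cycle 1.

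On size, the bias needs a linear rule that the documents do not specify. Recorded times would let an analyst avoid it, provided the late concentration is quantifiable. A reader might assume that it would usually be below quantification; with no assay limit or human half-life in the documents, that cannot be said.

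On dose, the case requires a DLT, a restart and a postponement in the same patient. A reader might infer that one such patient could be a whole dose group. After a DLT in a single-patient cohort, however, Table 2 expands that cohort up to 6 patients or until a second DLT.

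Finally, Section 9 calls itself a summary, and the SAP supplied consists of table and listing shells that refer to SAP text elsewhere. Dose normalisation may be specified there. Listing 16.1.7-1 records dose adjustments and the volume infused, so the correction is feasible.

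**Conclusion.** The point holds as a conflict to reconcile and a ratio to define. Footnotes 3 and 19 are incompatible for a postponed profile if the D6 allowance is used. The resulting error in the dosing-interval AUC is about +4 to +13% with linear interpolation at assumed half-lives of 2 to 12 hours, against +1 to +4% with an on-time sample. It is nil with log interpolation from actual times in a one-exponential model.

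The ratio formulas as written in Section 9.6.1 are wrong for a dose-reduced, postponed patient, by a factor of 0.50 or 0.69 to 0.79 under linear PK.

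A reader might go further and conclude that AUC and accumulation ratios are distorted for every postponed patient. The documents do not support that. A late draw is possible but not planned, it leaves the Cmax ratio alone, and a Day 5 AUC at a reduced dose is valid for the dose given. PK is a secondary, descriptive objective and the MTD rests on DLT counts, so this is a minor correction.

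**What to change.** 1. Reconcile footnotes 3 and 19: state that the +2-day D6 allowance does not apply to the 24-hour PK sample when the steady-state profile is taken in Cycle 2.
2. In Section 9.6.1 and the SAP, compute Day 5/Day 1 ratios on values divided by the mg actually infused, and compute AUC over 24 hours from actual sampling times with the interpolation rule named.
3. Add a Cycle 2 Day 5 row to Listings 16.2.6-1 and 16.2.6-2, and list and summarise postponed profiles as Cycle 2 Day 5 under the dose received.

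The cost is a footnote clause, a division by recorded dose and a change to the listing shells. Patients with a postponed profile lose D6 flexibility in one cycle. No dose or clinical rule changes.
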